6.5.1 Prior Treatment Details

The investigator or qualified designee will review all prior cancer treatments including systemic treatments, radiation and surgeries.

6.5.2 Subsequent Anti-Cancer Therapy Status

The investigator or qualified designee will review all new anti-neoplastic therapy initiated after the last dose of trial treatment. If a subject initiates a new anti-cancer therapy within 30 days after the last dose of trial treatment, the 30 day Safety Follow-up visit must occur before the first dose of the new therapy. Once new anti-cancer therapy has been initiated the subject will move into survival follow-up.

6.6 Clinical Procedures/Assessments

6.6.1 Adverse Event (AE) Monitoring

The investigator or qualified designee will assess each subject to evaluate for potential new or worsening AEs as specified in the Trial Flow Chart and more frequently if clinically indicated. Adverse experiences will be graded and recorded throughout the study and during the follow-up period according to NCI CTCAE Version 4.0. Toxicities will be characterized in terms regarding seriousness, causality, toxicity grading, and action taken with regard to trial treatment.

Please refer to section 10.2 for detailed information regarding the assessment and recording of AEs.

6.6.2 Physical Exam

The investigator or qualified designee will perform a complete physical exam during the screening period and directed physical exam for other visits. Clinically significant abnormal findings should be recorded as medical history.

6.6.3 Vital Signs

The investigator or qualified designee will take vital signs at screening, prior to the administration of each dose of trial treatment and at treatment discontinuation as specified in the Trial Flow Chart (Section 7.0). Vital signs should include temperature, pulse, respiratory rate, height, weight and blood pressure.

6.6.4 Eastern Cooperative Oncology Group (ECOG) Performance Scale

The investigator or qualified designee will assess ECOG performance status (see Section 7.0) at screening, prior to the administration of each dose of trial treatment and discontinuation of trial treatment as specified in the Trial Flow Chart.

6.6.5 Tumor Imaging and Assessment of Disease

CT scan or MRI (as indicated) will be performed at baseline (within 28 days of initiation of treatment) and after every 2 cycles. Brain MRI should be performed during screening. All scans will be subjected to RECIST 1.1 evaluation and modified RECIST (ir RECIST 1.1)

Participants in cohorts A and B should have brain MRI performed during standard planned radiologic assessment at the completion of chemotherapy.

Participants in cohort C and participants in cohort A and B who do not have brain metastases after completion of chemotherapy and DO NOT undergo prophylactic cranial irradiation should have brain MRI performed every 12 weeks during planned radiologic assessments (after completion of chemotherapy).

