4.1 Eligibility/Inclusion Criteria

1. Participants must have histologically confirmed small cell lung carcinoma not amenable to initial concurrent radiotherapy (extensive-stage disease).
2. Participants may have evaluable or measurable disease, defined as at least one lesion that can be accurately measured in at least one dimension (longest diameter to be recorded for non-nodal lesions and short axis for nodal lesions) as ≥ 20 mm with conventional techniques or as ≥ 10 mm with spiral CT scan, MRI, or calipers by clinical exam. See Section 7.0 for the evaluation of measurable disease.
3. Participants in cohort B must have completed 1 cycle of systemic chemotherapy. Therapy with the combination must start no sooner than 3 weeks from the last dose of chemotherapy and no later than 5 weeks from the last dose of chemotherapy. Participants in cohort B must not have had progression of disease prior to the start of therapy.
4. Participants in cohort C must have completed systemic therapy (4-6 cycles cisplatin or carboplatin + etoposides) and NOT be a candidate for consolidation thoracic radiotherapy or PCI. Participants in cohort C must initiate therapy with pembrolizumab within 6 weeks of the last dose of chemotherapy (therapy must not start within 2 weeks from the last dose). Participants in cohort C must not have had progression of disease prior to the start of therapy.
5. Participants in cohort D must have completed systemic therapy AND have completed either consolidation thoracic radiotherapy or PCI or both completed either consolidation thoracic radiotherapy or PCI or both. Participants in cohort D must initiate therapy with pembrolizumab within 6 weeks of the last dose of radiation. Therapy must not start within 2 weeks from the

last dose. **Consolidation radiotherapy dose must NOT be more than 3000 cGy.**
 Participants in cohort D must not have had progression of disease prior to the start of therapy.

6. Age > 18 years.
7. ECOG performance status ≤ 2 (Karnofsky $\geq 60\%$, see Appendix A)
8. Life expectancy of greater than 3 months.
9. Participants must have normal organ and marrow function during screening and on Cycle 1, day 1 as defined below:

Table 1 Adequate Organ Function Laboratory Values

System	Laboratory Value
Hematological	
Absolute neutrophil count (ANC)	$\geq 1,500$ /mcL
Platelets	$\geq 100,000$ / mcL
Hemoglobin	≥ 9 g/dL or ≥ 5.6 mmol/L without transfusion or EPO dependency (within 7 days of assessment)
Renal	

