Serum creatinine OR Measured or calculated ^a creatinine clearance (GFR can also be used in place of creatinine or CrCl)	≤ 1.5 X upper limit of normal (ULN) OR ≥ 60 mL/min for subject with creatinine levels > 1.5 X institutional ULN
Hepatic	
Serum total bilirubin	≤ 1.5 X ULN OR Direct bilirubin \leq ULN for subjects with total bilirubin levels > 1.5 ULN
AST (SGOT) and ALT (SGPT)	≤ 2.5 X ULN OR ≤ 5 X ULN for subjects with liver metastases
Albumin	≥ 2.5 mg/dL
Coagulation	
International Normalized Ratio (INR) or Prothrombin Time (PT)	≤ 1.5 X ULN unless subject is receiving anticoagulant therapy as long as PT or PTT is within therapeutic range of intended use of anticoagulants
Activated Partial Thromboplastin Time (aPTT)	≤ 1.5 X ULN unless subject is receiving anticoagulant therapy as long as PT or PTT is within therapeutic range of intended use of anticoagulants
^a Creatinine clearance should be calculated per institutional standard.	

10. Availability of a diagnostic or pre-chemotherapy tissue biopsy is required (cytologic specimens or bone biopsies not accepted). This biopsy must be within 6 weeks of starting initial therapy. A minimum of 20 5 µm slides or block is required.
11. Participants in cohorts B-D must be willing to provide tissue from a newly obtained core or excisional biopsy of a tumor lesion. Newly-obtained is defined as a specimen within 4 weeks to initiation of treatment and AFTER the last dose of any prior therapy.
12. Participants with treated brain metastases are allowed. Radiation must be completed at least 2 weeks prior to pembrolizumab dosing and participants must not require ongoing steroids. Participants with untreated brain metastases that are all <5 mm with no clinical symptoms or vasogenic edema may be allowed on study on a case-by-case basis on discussion with sponsor. These participants will require MRI monitoring every 6 weeks to ensure stability.

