6.7.5.2 Collection, Handling, Shipping, and Site Performing analyses for circulating free DNA

For cf DNA samples, blood will be collected in 10 cc EDTA tubes, barcoded, and processed within 3 hours of blood draw. We have previously confirmed that white blood cells remain stable during this period of time and thus, do not affect the purity of tumor-derived cell-free DNA. 1mL of whole blood will be banked from each tube and frozen at -80C in a 2d-barcoded tube until further processing. The remaining blood will be subjected to two rounds of centrifugation (2,000 x g for 10 min followed by 15,000 x g for 10min). Plasma will be removed and frozen at -80C in another 2d-barcoded tube until further processing. All samples are registered in our laboratory information management system and tracked throughout the process. Extractions of cell-free DNA and germline DNA will be performed from banked plasma and whole blood, respectively, using an automated liquid handler. Liquid handling systems will also be used for the subsequent steps of quantification, normalization, and library construction. Sequencing on the Illumina HiSeq will be used to assess the purity of tumor-derived cell-free DNA. Samples with sufficient purity of tumor-derived cell-free DNA will be nominated for hybrid capture of the entire human exome and sequenced on the Illumina HiSeq.

Samples should be shipped on dry ice to:

The Broad Institute
Attn: Blood Biopsy Group
[name]
Lab 4045
[name]

7 Study Calendar/Protocol Flow Chart

Baseline evaluations are to be conducted within 21 days prior to start of protocol therapy. Scans and x-rays must be done ≤ 28 days prior to the start of therapy.

Assessments must be performed prior to administration of any study agent. Study assessments and agents should be administered within ± 3 days of the protocol-specified date, unless otherwise noted.

Study Calendar/Protocol Flow Chart Cohort A and B

	Screening (days --28 to 0)	C1 ^a	C2	C3-6 ^b	Maintenance Pembro ^c C1-34	End of Treatment	Post-Treatment			Second Course phase (Retreatment)
							Safety Follow-up	Follow-up	Survival follow-up	
Pembrolizumab		A	A	A	A		Safety Follow-up	Follow-up	Survival follow-up	A
Cisplatin or Carboplatin ¹		B	B	B						
Etoposide ²		C	C	C						
Informed consent	X									X ^h
Demographics	X									
Medical history	X									X
Concurrent meds	X	X	X	X	X	X				X
Details of prior therapy for cohort B	X									
Physical exam	X	X	X	X	X	X		X ^g		X

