8.1.3 Methods for Evaluation of Disease

All measurements should be taken and recorded in metric notation using a ruler, calipers, or a digital measurement tool. All baseline evaluations should be performed as closely as possible to the beginning of treatment and never more than 4 weeks before the beginning of the treatment.

The same method of assessment and the same technique should be used to characterize each identified and reported lesion at baseline and during follow-up. Imaging-based evaluation is preferred to evaluation by clinical examination unless the lesion(s) being followed cannot be imaged but are assessable by clinical exam.

Clinical lesions. Clinical lesions will only be considered measurable when they are superficial (e.g., skin nodules and palpable lymph nodes) and ≥ 10 mm in diameter as assessed using calipers (e.g., skin nodules). In the case of skin lesions, documentation by color photography, including a ruler to estimate the size of the lesion, is recommended.

Chest x-ray. Lesions on chest x-ray are acceptable as measurable lesions when they are clearly defined and surrounded by aerated lung; however, CT is preferable.

Conventional CT and MRI. This guideline has defined measurability of lesions on CT scan based on the assumption that CT thickness is 5mm or less. If CT scans have slice thickness greater than 5 mm, the minimum size of a measurable lesion should be twice the slice thickness. MRI is also acceptable in certain situations (e.g. for body scans).

Use of MRI remains a complex issue. MRI has excellent contrast, spatial, and temporal resolution; however, there are many image acquisition variables involved in MRI, which greatly impact image quality, lesion conspicuity, and measurement. Furthermore, the availability of MRI is variable globally. As with CT, if an MRI is performed, the technical specifications of the scanning sequences used should be optimized for the evaluation of the type and site of disease. Furthermore, as with CT, the modality used at follow-up should be the same as was used at baseline and the lesions should be measured/assessed on the same pulse sequence. It is beyond the scope of the RECIST guidelines to prescribe specific MRI pulse sequence parameters for all scanners, body parts, and diseases. Ideally, the same type of scanner should be used and the image acquisition protocol

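### In cohorts B-D the baseline scan may predate the last chemotherapy or radiation dose, so earlier shrinkage can delay target-lesion progression and overstate response

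*Combined protocol and SAP*

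**What the plan says.** Four places set the timing of the baseline scan, and each gives only a maximum age.

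- Section 6.6.5: "CT scan or MRI (as indicated) will be performed at baseline (within 28 days of initiation of treatment) and after every 2 cycles".
- Section 6.6.9.1 repeats the 28-day limit for scans.
- Section 7, introduction to the calendars: "Scans and x-rays must be done ≤ 28 days prior to the start of therapy".
- Section 8.1.3 says of the baseline measurements that they "should be performed as closely as possible to the beginning of treatment and never more than 4 weeks before the beginning of the treatment". The first half of that sentence is a preference; only the 4-week limit binds.

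Section 4.1 sets the gap between prior therapy and study treatment. For cohort B: "Therapy with the combination must start no sooner than 3 weeks from the last dose of chemotherapy and no later than 5 weeks". Cohorts C and D may start from 2 to 6 weeks after their last chemotherapy or radiation dose.

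For the new biopsy in cohorts B-D, section 4.1 item 11 adds a second condition: "Newly-obtained is defined as a specimen within 4 weeks to initiation of treatment and AFTER the last dose of any prior therapy". The calendar footnotes repeat it. No scan rule contains it.

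Section 8.1.4.1 measures partial response from the baseline sum, and progression from the smallest sum on study, baseline included. Section 8.2.2 (irRECIST) likewise uses baseline for response and nadir for progression. Section 3.3 defines PFS for the overall population, stratified by cohort and set against 5.4 months.

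**The concern.** The baseline scan should show the tumour as it stands when pembrolizumab starts. In cohorts B-D the 28-day window is longer than the shortest permitted gap after prior therapy. A scan can therefore obey every rule and still show the tumour before the last chemotherapy cycle was finished, or before radiation was finished. Sections 1.7 and 6.7.1.1 themselves describe SCLC as highly responsive to both.

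Shrinkage between such a scan and the first dose leaves a recorded baseline sum that is too large. Two errors follow. Regrowth on pembrolizumab must first make up the unrecorded shrinkage before target-lesion progression is scored, so PFS in that participant may be prolonged. And shrinkage caused by prior therapy may be scored as response on study. Cohort A has no prior therapy and is free of both errors, so the distortion differs between the cohorts by which PFS is stratified.

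**Working it through.** The plan gives no figure for this point. Its one power figure, 88% for the paired PD-L1 test (section 9.1; 12 per cohort, effect size 1.0, two-sided 0.05), is closely reproduced: 88.3% for a paired t-test, and 87.6% (normal-approximation critical value) or 85.2% (exact) for a simulated signed-rank test. It does not depend on the scan.

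**Step 1: how early can a compliant scan be?** Inputs: scan window 28 days (6.6.5, 7, 8.1.3); start windows from section 4.1. Maximum lead of the scan over the last prior dose = 28 − shortest gap. Share of the start window exposed = (28 − shortest gap) / (longest gap − shortest gap).

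| Cohort | Start, days after last dose | Maximum lead | Exposed starts | Share of window |
|---|---|---|---|---|
| B | 21-35 | 28 − 21 = 7 days | days 21-27 | 7/14 = half |
| C | 14-42 | 28 − 14 = 14 days | days 14-27 | 14/28 = half |
| D | 14-42 | 28 − 14 = 14 days | days 14-27 | 14/28 = half |

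From day 28 onward no overlap is possible. The last column is a share of permitted days, not of participants.

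Etoposide runs to day 3 of a cycle. Under section 4.1, day 1 of the last prior cycle is therefore at least 21 + 2 = 23 days (B) or 14 + 2 = 16 days (C) before the start. A scan can precede that whole cycle by up to 28 − 23 = 5 days (B) or 28 − 16 = 12 days (C). Section 5.3 instead counts B and C from the start of the last cycle, which turns 5 and 12 into 7 and 14. The two sections need reconciling, but overlap exists under either. In cohort D, assume 10 fractions (5.5.7) given five per week and ending 14 days before the start. The first fraction then falls 14 + 11 = 25 days before the start, and a scan 26 to 28 days before it precedes the whole course.

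**Step 2: what would unrecorded shrinkage do?** Let the recorded baseline be 100 mm and *s* the assumed shrinkage between scan and first dose. Size at first dose = 100(1 − *s*). With baseline as the smallest sum, progression needs 120 mm (the 5 mm condition is then met). Regrowth needed = 1.20/(1 − *s*) − 1. With no change on study, the scored change is −*s*.

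| *s* (assumed) | Size at first dose | Regrowth needed for PD | Scored if nothing changes |
|---|---|---|---|
| 10% | 90 mm | 33% | −10%, SD |
| 20% | 80 mm | 50% | −20%, SD |
| 30% | 70 mm | 71% | −30%, PR |
| 40% | 60 mm | 100% | −40%, PR |

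With a correct baseline the threshold is 20% regrowth. A true 20% regrowth is scored as PR once 1.20(1 − *s*) ≤ 0.70, that is *s* ≥ 1 − 0.70/1.20 = 41.7%.

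These regrowth figures apply at the first on-study scan. If that scan is below the recorded baseline it becomes the new reference, which limits how long the error lasts. One assessment interval is 6 weeks, or 42/30.4 = 1.4 months.

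**Step 3: after the fix.** If the scan must also follow the last prior dose, the overlap is 0 in all three cohorts. The section 4.1 windows still leave at least 21 (B), 14 (C) and 14 (D) days for the scan.

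**The case against.** Several objections narrow the point; none removes it.

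- **Response endpoint.** A reader might infer that the trial's response-rate endpoint is biased. Section 3.3 restricts that endpoint to cohort A, which is unaffected. The exposure is in the section 2.2 response objective, which has no cohort limit, and in the PD-L1/response comparison in section 9.1.
- **Eligibility.** A reader might infer that the entry checks rest on the same early scan. The documents do not say so. Rules such as "Participants in cohort D must not have had progression of disease prior to the start of therapy" name no scan. The exclusion of complete responders (4.2), stable disease in cohort C (5.3) and that cohort's CT for initial response (6.4.3) all imply some assessment after prior therapy. None of them dates it or makes it the RECIST baseline.
- **PFS.** It is tempting to say that PFS gains at least one 6-week interval. That is too strong. New lesions, unequivocal non-target progression and death still count on time. A lesion that arose between an early scan and the first dose would be counted as progression on study, which pulls the other way. The net effect on median PFS is not determined.
- **Worst case.** The largest overlap needs the earliest start and the oldest permitted scan. Laboratory limits, toxicity recovery and the new biopsy make very early starts harder, and section 8.1.3 asks for scans near the start. This bears on frequency; a preference does not exclude an early scan, and section 4.5.1 allows standard-of-care procedures before consent.
- **Cohort differences.** Cohort D participants given only cranial irradiation have no thoracic radiation effect. Section 8.1.2 leaves open whether irradiated lesions are measurable. In cohort B chemotherapy continues on study and the overlap is shorter.

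**Conclusion.** The gap is real and follows from the plan's own windows. For starts before day 28 after the last prior dose, a compliant baseline scan can predate that dose by up to 7 days (B) or 14 days (C, D). Such a scan can delay target-lesion progression, and so PFS, and can overstate RECIST and irRECIST response in these cohorts.

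The size cannot be computed. The documents give neither shrinkage figures nor the expected number of early scans; the 10% to 40% used above is an assumed range. Under it, target-lesion progression needs 33% to 100% regrowth instead of 20%, and a partial response without on-study change appears from 30%. The primary PD-L1 endpoint has its own timing rule and is unaffected, as are its power and the section 3.3 response endpoint. The point concerns secondary outcomes and merits correction because the remedy is simple and the plan already uses it for tissue.

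**What to change.** In section 6.6.5, in section 7 (both calendars) and in section 8.1.3, add for cohorts B-D: the RECIST baseline scan must be within 28 days before the first pembrolizumab dose and after the last dose of prior chemotherapy or radiation. This mirrors the biopsy condition in section 4.1 item 11.

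For participants already enrolled, flag every baseline scan that predates the last prior dose, and report PFS and response with and without those participants.

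The cost is one sentence in each place. Some screening scans move later in the window, and an early routine scan intended as baseline may occasionally have to be repeated. Sample size and treatment rules do not change.

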6.6.6 Pulmonary Function Tests

A baseline set of pulmonary function tests including DLCO will be obtained during screening.

6.6.7 Tumor Tissue Collection and Correlative Studies Blood Sampling

6.6.7.1 Tumor Tissue Collection

For cohort A, an archival (diagnostic) tissue biopsy obtained within six weeks of study start (minimum 20 5 um slides) will be required. For cohorts B-D, an archival (diagnostic) tissue biopsy (minimum 20 5 um slides) will be required (prior to initiation of any treatment). In addition, for cohorts B-D, a new core tissue biopsy (minimum 3 cores from lung tissue, minimum 4 cores from any other site) will be required prior to study entry.

A minimum of 4 participants in each cohort (B-D) will be required to have fresh tissue sampling from which FNA will be also obtained for immune profiling at the Belfer Institute. For those participants, FNA will be immediately placed into RPMI media and hand-couriered to the Belfer Institute ([name] at DFCI) or to the [name] laboratory at NYU. The remaining core biopsies of fresh tissue will be formalin-fixed and paraffin-embedded as per institutional standards for further evaluation with IHC or tumor DNA/RNA extraction for sequencing or nanostring and shipped to the Overall PI, [name] (see also section 6.7.2.1).

Optional core biopsies will be obtained at the time of tumor progression from participants who consent to this procedure. A minimum of 3 cores will be required.

6.6.7.2 Correlative Studies Blood Sampling

10 ml of blood for evaluation of soluble PD-L1 (and possibly for additional cytokine profiling) will be obtained at screening, cycle 2 day 1, every other cycle day 1 thereafter, and at the time of progression.

6.6.8 Laboratory Procedures/Assessments

Details regarding specific laboratory procedures/assessments to be performed in this trial are provided below. Screening assessments other than scans should take place within 21 days of study entry. Laboratory Safety Evaluations (Hematology, Chemistry and Urinalysis)
Laboratory tests for hematology, chemistry, urinalysis, and others are specified in Table 5.

Table 5 Laboratory Tests to be performed during screening

Hematology	Chemistry	Urinalysis ^b	Other
Hematocrit	Albumin	Blood	Serum β -human chorionic gonadotropin ^a
Hemoglobin	Alkaline phosphatase	Glucose	(β -hCG) [†]
Platelet count	Alanine aminotransferase (ALT)	Protein	PT (INR) ^b
WBC (total and differential)	Aspartate aminotransferase (AST)	Specific gravity	aPTT ^b
Red Blood Cell Count	Lactate dehydrogenase (LDH)	Microscopic exam (If abnormal)	Total triiodothyronine (T3) ^c
Absolute Neutrophil Count	Carbon Dioxide	results are noted	Free tyroxine (T4) ^c
Absolute Lymphocyte Count	(CO ₂ or biocarbonate)	Urine pregnancy test ^a	Thyroid stimulating hormone (TSH) ^c
	Uric Acid ^b		
	Calcium		
	Chloride		Blood for correlative studies
	Glucose		
	Phosphorus		
	Potassium		
	Sodium		
	Magnesium		
	Total Bilirubin		
	Direct Bilirubin (If total bilirubin is elevated above the upper limit of normal)		
	Total protein		
	Blood Urea Nitrogen		

^a Perform on women of childbearing potential only during screening and after every 4 cycles. If urine pregnancy results cannot be confirmed as negative, a serum pregnancy test will be required.

^b During screening only and as clinically indicated thereafter.

^c TSH to be obtained every 2 cycles and T3/T4 to be obtained at screening and if TSH abnormal thereafter.

Laboratory tests for screening or entry into the Second Course Phase should be performed within 10 days prior to the first dose of treatment. After Cycle 1, pre-dose laboratory procedures can be conducted up to 72 hours prior to dosing. Results must be reviewed by the investigator or qualified designee and found to be acceptable prior to each dose of trial treatment.

